18.0 Records and Data Collection Procedures

18.1 Submission Timetable

Initial Material(s)

Case Report Form (CRF)	Active-Monitoring Phase (Compliance with Test Schedule Section 4.0)
On-Study	≤ 2 weeks after registration
Adverse Event - Baseline	
Research Blood Submission	
Research Bone Marrow Submission	
Measurement Bone Marrow and Biopsy - Baseline	
Bone Marrow Biopsy and Aspirate Report including the FLT3 mutation by PCR and cytogenetics.	Submit ≤ 2 weeks after registration if withdrawal/refusal occurs prior to beginning protocol therapy
End of Active Treatment/Cancel Notification	

Test Schedule Material(s)

CRF	Active-Monitoring Phase (Compliance with Test Schedule Section 4.0)	
	At each evaluation during treatment	At end of treatment
Evaluation/Treatment	X	X
Nadir/Adverse Event	X	X
Measurement and Disease Response	X	X
Bone Marrow Biopsy and Aspirate Report including the FLT3 mutation by PCR and cytogenetics	X ¹	X
Research Blood Submission	X ¹	
Research Bone Marrow Submission	X ¹	
End of Active Treatment/Cancel Notification		X
ADR/AER	At each occurrence (see Section 10.0)	

1. Only when required by the Test Schedule (see Section 4.0 and 14.0)).

Follow-up Material(s)

CRF	Event Monitoring Phase ¹				
	q. 6 months until PD ²	At PD ²	After PD q. 6 mos.	Death	New Primary
Event Monitoring	X	X	X	X	At each occurrence

1. If a patient is still alive 2 years after registration, no further follow-up is required.
2. Submit copy of documentation of response or progression to the MCCC Operations Office, Attention: QAS for MC1483.

19.0 Budget

- 19.1 Costs charged to patient: routine clinical care.
- 19.2 Tests to be research funded: Study drug, urinalysis, ECG, blood and aspirate correlatives.
- 19.3 Other budget concerns: Protocol administration, data management and statistical analysis efforts will be by funded by Novartis.

Appendix Ia: Drugs with Risk of Torsades de Pointes

This list contains medications that are generally accepted (and documented in published data) as having an increased risk of QT prolongation and/or torsades de pointes. Concomitant administration of midostaurin and a medication on this list is **prohibited**.

Generic Name	Brand Name	Comments
Amiodarone	Cordarone®, Pacerone®	Low risk torsades de pointes
Arsenic trioxide	Trisenox®	Torsades de pointes
Bepidil	Vasocor®	
Chloroquine	Aralen®	
Chlorpromazine	Thorazine®	
Cisapride	Propulsid®	Restricted availability in U.S.
Clarithromycin	Biaxin®	
Disopyramide	Norpace®	Torsades de pointes
Dofetilide	Tikosyn®	Torsades de pointes
Dolasetron	Anzemet®	
Droperidol	Inapsine®	Torsades de pointes
Erythromycin	Erythrocin®, E.E.S. ®	IV > PO
Halofantrine	Halfan®	
Haloperidol	Haldol®	IV > PO, high doses increase QT prolongation and torsades de pointes
Ibutilide	Corvert®	Torsades de pointes, female > male, non-Caucasian > Caucasian
Levomethadyl	Orlaam®	
Mesoridazine	Serentil®	
Methadone	Dolophine®, Methadose®	
Pentamidine	Pentam®, Nebupent®	
Pimozide	Orap®	
Procainamide	Pronestyl®, Procan®, Procanbid®	N-acetylprocainamide causes torsade de pointes, not parent compound
Quinidine	Cardioquin®, Quinaglute®	Torsades de pointes
Sotalol	Betapace®	Torsade de pointes female > male
Sparfloxacin	Zagam®	
Thioridazine	Mellaril®	

Note: the above list is not all-inclusive.

References:

Kies SJ, Pabelick CM et al. Anesthesia for Patients with Congenital Long QT Syndrome. *Anesthesiology* 2005;102:204-210

Roden DM. Drug-Induced Prolongation of the QT Interval. *The New England Journal of Medicine* 2004;350:1013-1022.

<http://www.azcert.org/medical-pros/druginteractions.cfm> Accessed 5/13/11

Appendix Ib: Drugs with Possible or Conditional Risk of Torsades de Pointes

This list contains medications that, in some reports, have been associated or weakly associated with causing torsades de pointes and/or QT prolongation. There is insufficient data that these medications alone may cause torsades de pointes and/or QT prolongation, however when midostaurin is given concomitantly with a medication on this list (or other risk factors are present such as bradycardia, electrolyte disturbances, congenital long QT syndrome, or concomitant drugs that inhibit metabolism), there may be possible or conditional risk of torsades de pointes and/or QT prolongation. Extreme caution and careful monitoring should be instituted with concomitant administration of midostaurin and a medication on this list.

Generic Name	Brand Name	Comments
Alfuzosin	Uroxatral®	
Amantadine	Symmetrel®	Low
Amitriptyline	Elavil®	Nonspecific ECG changes reported.
Atazanavir	Reyataz®	
Azithromycin	Zithromax®	
Chloral hydrate	Noctec®	
Ciprofloxacin	Cipro®	
Citalopram	Celexa®	
Clomipramine	Anafranil®	
Desipramine	Pertofrane®	QT prolongation, VF/sudden death reported
Diphenhydramine	Benadryl®, Nytol®	
Dolasetron	Anzemet®	Granisetron < Ondansetron < Dolasetron
Doxepin	Sinequan®	
Dronedarone	Multaq®	
Escitalopram	Lexapro®, Cipralextm	
Felbamate	Felbatrol®	
Flecainide	Tambocor®	
Foscarnet	Foscavir®	
Fosphenytoin	Cerebyx®	
Fluconazole	Diflucan®	IV > PO
Fluoxetine	Prozac®, Sarafem®	1 in 10,000 ventricular arrhythmias reported
Galantamine	Reminyl®	
Gatifloxacin	Tequin®	
Gemifloxacin	Factive®	
Granisetron	Kytril®	Granisetron < Ondansetron < Dolasetron
Imipramine	Norfranil®	Nonspecific arrhythmias reported
Indapamide	Lozol®	
Isradipine	Dynacirc®	
Itraconazole	Sporanox®	
Ketoconazole	Nizoral®	
Lapatinib	Tykerb®	
Levofloxacin	Levaquin®	Lower risk than that of similar agents
Lithium	Lithobid®, Eskalith®	
Moexipril/HCTZ	Uniretic®	

Moxifloxacin	Avelox®	
Nicardipine	Cardene®	
Nilotinib	Tasigna®	
Nortriptyline	Pamelor®	Nonspecific arrhythmias reported
Octreotide	Sandostatin®	
Ofloxacin	Floxin®	
Ondansetron	Zofran®	Granisetron < Ondansetron < Dolasetron
Oxytocin	Pitocin®	
Paliperidone	Invega®	
Paroxetine	Paxel®	Lower risk than TCA's
Perflutren lipid microspheres	Definity®	
Protriptyline	Vivactil®	
Quetiapine	Seroquel®	QT prolongation
Ranolazine	Ranexa®	
Risperidone	Risperdal®	QT prolongation, sudden death reported
Ritonavir	Norvir®	
Sertraline	Zoloft®	Lower risk than TCA's
Solifenacin	VESIcare®	
Sunitinib	Sutent®	
Tacrolimus	Prograf®	
Tamoxifen	Nolvadex®	
Telithromycin	Ketek®	
Tizanidine	Zanaflex®	
Trazodone	Desyrel®	
Trimethoprim-Sulfa	Sulfa®, Bactrim®, Bactrim DS®	Low
Trimipramine	Surmontil®	
Vardenafil	Levitra®	
Venlafaxine	Effexor®	1 :1000 risk of arrhythmia reported
Voriconazole	VFend®	
Ziprasidone	Geodon®	QT prolongation, 1:1000 risk of arrhythmia

Note: the above list is not all-inclusive.

References:

Kies SJ, Pabelick CM et al. Anesthesia for Patients with Congenital Long QT Syndrome. *Anesthesiology* 2005;102:204-210

Roden DM. Drug-Induced Prolongation of the QT Interval. *The New England Journal of Medicine* 2004;350:1013-1022.

<http://www.azcert.org/medical-pros/druginteractions.cfm> Accessed 5/13/11

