 - History of Congestive heart failure requiring use of ongoing maintenance therapy for life-threatening ventricular arrhythmias.
- 3.29a Patients currently receiving treatment with strong CYP3A4 inhibitors

and treatment that cannot be either discontinued or switched to a different medication prior to starting study drug. Patients receiving any medications or substances that are strong inhibitors of CYP3A4. All Azoles but fluconazole are discouraged to be used in patients requiring treatment with antifungal antibiotics.

Use of the following strong inhibitors is prohibited ≤ 7 days prior to registration.

Strong Inhibitors of CYP3A4/5 > 5-fold increase in the plasma AUC values or more than 80% decrease in clearance
Boceprevir (Victrelis®) Clarithromycin (Biaxin®, Biaxin XL®) Conivaptan (Vaprisol®) Indinavir (Crixivan®) Itraconazole (Sporanox®) Ketoconazole (Nizoral®) Lopinavir/Ritonavir (Kaletra®) Mibefradil Nefazodone (Serzone®) Nelfinavir (Viracept®) Posaconazole (Noxafil®) Ritonavir (Novir®, Kaletra®) Saquinavir (Fortovase®, Invirase®) Telaprevir (Incivek®) Telithromycin (Ketek®) Voriconazole (Vfend®) troleandomycin cobicistat tipranavir

3.29b Receiving any medications or substances that are **inducers** of CYP3A4. Use of the following inducers are prohibited ≤ 7 days prior to registration.

Strong Inducers of CYP3A4/5 > 80% decrease in AUC
Avasimibe Carbamazepine (Carbatrol®, Eptol®, Equetro™, Tegretol®, Tegretol-XR®) Phenytoin (Dilantin®, Phenytek®) Rifampin (Rifadin®) St. John's wort mitotane rifabutin phenobarbital
Moderate Inducers of CYP3A4/5 50-80% decrease in AUC
Bosentan (Tracleer®) Efavirenz (Sustiva®)

Etravirine (Intelence®) Modafinil (Provigil®) Nafcillin Genistein Ritonavir Talyraline Thioridazine Tipranavir Nevirapine (Viramune®) Phenobarbital (Luminal®) Rifabutin (Mycobutin®) Troglitazone

- 3.29c Patients currently receiving treatment with any medications that have the potential to prolong the QT interval and the treatment cannot be either discontinued or switched to a different medication prior to starting study drug. NOTE: Prohibited medications are listed in Appendix Ia “Drugs With Risk of Torsades de Pointes.” Appendix Ib contains drugs that should be used with caution due to possible or conditional risk of Torsades de Pointes.

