- 15.191 Patients should be instructed to take medication at the same time every day, twice daily with food. Capsules must be swallowed whole with a glass of water and cannot be chewed or crushed. Oral solution is available for pediatric patients—follow separate preparation instruction in section 15.14. Medicine must be properly disposed of. Do not pour down a sink or toilet. Wipe up spills immediately. Avoid skin contact.
- 15.192 Assess patient's concomitant medications, including OTC and herbal products. Midostaurin has interactions with drugs that are metabolized via CYP3A4 and caution should be exercised for patients who are on these agents. For more details refer to section 15.16 of the protocol.
- 15.193 Gastrointestinal side effects are common, including nausea, vomiting, and diarrhea. Treat symptomatically and monitor for effectiveness. Patients should be premedicated for the prevention of nausea and vomiting.
- 15.194 Monitor creatinine and renal function as renal impairment/failure has been seen.
- 15.195 Instruct patients to report any signs/symptoms of CHF/LVEF dysfunction, including chest pain, SOB, and edema.
- 15.196 Monitor CBC w/diff as cytopenias can be seen. Instruct patients to report any signs/symptoms of infection and/or any unusual bruising/bleeding to the study team.
- 15.197 Monitor glucose levels per protocol as hyperglycemia has been seen. Diabetics may need additional monitoring.

15.198 Back pain and arthralgia's have been seen. Treat symptomatically and monitor for effectiveness.

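### Dolasetron is on both the prohibited list (Appendix Ia) and the caution list (Appendix Ib), so the protocol gives conflicting instructions for one antiemetic

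*Combined protocol and SAP*

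**What the plan says.** Exclusion criterion 3.29c in Section 3.2 gives the two appendices different roles. For one it says "Prohibited medications are listed in Appendix Ia". For the other it says "Appendix Ib contains drugs that should be used with caution due to possible or conditional risk of Torsades de Pointes".

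The appendix headers repeat that division and give the reasons for it:

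- **Appendix Ia** describes its drugs as "generally accepted (and documented in published data) as having an increased risk of QT prolongation and/or torsades de pointes". Its rule is "Concomitant administration of midostaurin and a medication on this list is" prohibited (the last word is in bold in the protocol). Dolasetron (Anzemet) has a row with an empty comment cell.
- **Appendix Ib** says of its drugs: "There is insufficient data that these medications alone may cause torsades de pointes and/or QT prolongation". Its rule is "Extreme caution and careful monitoring should be instituted with concomitant administration of midostaurin and a medication on this list". Dolasetron (Anzemet) has a row here too. Its comment, "Granisetron < Ondansetron < Dolasetron", is repeated in the granisetron and ondansetron rows.

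No section outside the two appendices names dolasetron. Section 9.1 leaves antiemetics to the attending physician and names no drug. The nursing guidelines call for antiemetic premedication with both agents: 15.193 for midostaurin ("Patients should be premedicated for the prevention of nausea and vomiting") and 15.29 for decitabine.

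**The concern.** A drug cannot be both barred and usable with caution. The stated evidence conflicts as well: Ia treats the risk as established, and Ib says the data are insufficient for the drug alone.

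The conflict falls on a routine decision. Premedication is expected with both study drugs, the choice is left to the physician, and the appendices are the only drug-specific QT guidance that a prescriber has. All three setrons appear together, with a ranking, only in Ib. Someone choosing among them there could take dolasetron as allowed with caution and not check Ia. Under Section 7.1, decitabine on days 2-5 may also be given by a local physician outside the centre.

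At stake is avoidable exposure to a drug with QT liability alongside midostaurin, whose own QTc effect Section 8.2 describes as not yet fully characterised.

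**Working it through.** This is a comparison of texts. The plan states no figure for this point, so there is none to reproduce.

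**Step 1: extent of the overlap.** The generic names in the two appendices were transcribed and compared.

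| | As written | Ib dolasetron row deleted |
|---|---|---|
| Rows in Ia | 25 | 25 |
| Rows in Ib | 64 | 64 − 1 = 63 |
| Names in both | 1 (dolasetron) | 0 |
| Distinct drugs | 25 + 64 − 1 = 88 | 25 + 63 − 0 = 88 |

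Dolasetron is the only shared name. Deleting the Ib row removes the overlap and no drug loses its listing. Deleting the Ia row would also remove it (24 + 64 = 88), so the count cannot show which row is wrong.

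**Step 2: which actions comply.**

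| Action | Appendix Ia and 3.29c | Appendix Ib |
|---|---|---|
| Avoid dolasetron | complies | complies (Ib does not require its use) |
| Give dolasetron with caution and monitoring | breaches | complies |

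Only avoidance satisfies both lists.

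**Step 3: evidence of intent.** The ranking comment in Ib does not say what it ranks. Read most naturally, it puts dolasetron as the highest-risk setron, which fits Ia. But it is a class-level remark repeated in three rows, and it neither prohibits nor permits. The empty comment cell in Ia says little, since 13 of the 25 Ia rows have none. Neither feature settles the matter.

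**Step 4: existing safeguards.**

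- Section 4.0 requires an ECG at screening, on Day 8 of each cycle before dosing (on Day 1 from cycle 2 if midostaurin starts then), and at end of treatment.
- Footnote 3 of Section 4.0 adds ECGs for QTc-related dose changes and for restarts after an interruption.
- The note under 8.2 is wider: an ECG 7 days after any dose change.
- Potassium and magnesium are checked repeatedly (4.0), and a confirmed baseline QTc above 450 msec excludes the patient (3.28).
- Section 8.2 calls for stopping QT-prolonging medication where possible once the QTc is prolonged, and 15.192 tells nurses to assess concomitant medication.

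These limit the consequence. The dose and medication rules in 8.2 act only after prolongation has been found. On the standard days 8-21 schedule, the scheduled ECG in each cycle comes before that cycle's midostaurin.

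**Step 5: effect on the design.** The target of 24 evaluable patients, the significance level of .09 and the power of 0.89 at a 30% success rate depend only on the binomial rule of 5 or more successes in 24. Recomputing that rule gives 0.0851 at 10% and 0.8889 at 30%, matching the plan's rounded figures. The drug lists do not enter.

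**The case against.** The strongest reply is that the text already resolves the conflict in practice. Section 3.29c says where the prohibited drugs are listed, and the Ia header bars them without condition. Ib never says that its drugs are permitted. Nor is an Ib row clearance elsewhere: ketoconazole, itraconazole, voriconazole, ritonavir and telithromycin are in Ib, yet 3.29a prohibits them within 7 days before registration. For dolasetron to be given, a prescriber would have to read Ib and overlook both Ia and 3.29c.

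Much of this stands. It supports prohibition as the working rule and keeps the point minor. It does not remove the inconsistency. The 3.29a restriction rests on a different ground (CYP3A4 inhibition) and a pre-registration window, so it does not explain why one drug sits in two QT categories that 3.29c separates.

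A second objection concerns the remedy. A reader might infer that the Ib row is plainly the drafting error. The documents do not support that. Deleting either row clears the overlap, the Ib row is the one with a comment, and both appendices cite the same references, which are not available here. If Ib was intended, deleting its row would make a mistaken ban permanent. That objection stands, and it is why the sponsor should have the chance to say that the Ia row was unintended.

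**Conclusion.** The inconsistency is real and confined to one antiemetic among 88 listed drugs. Two operative safety lists give it conflicting instructions, and no other section resolves the conflict. Which row was intended is not established. Prohibition is nevertheless the right default: it is stated outright in two places, and it is the only course that complies with both lists.

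A reader might also infer that patients have been or will be harmed. The documents give no figure for dolasetron use, so the number of patients exposed cannot be estimated, and the ECG and QTc rules limit the consequence. Eligibility is barely affected, because 3.29c excludes a patient only when the QT-prolonging drug cannot be stopped or switched. Sample size, alpha, power and the primary analysis are unaffected.

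The conclusion rests on the two tables being read as printed. The relevant rows are complete and legible.

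**What to change.** Ask the sponsor to state dolasetron's status, and treat it as prohibited in the meantime. Unless the sponsor confirms that the Ia row was unintended:

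- delete the dolasetron row from Appendix Ib;
- in the granisetron and ondansetron comment cells of Ib, add that dolasetron is prohibited, with a reference to Appendix Ia.

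If the sponsor does confirm that Ia was wrong, the Ia row should go instead, so that the drug still has one status and one row.

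The default fix costs one deleted row, two edited cells and the administrative work of an amendment, which can be combined with the next one. It keeps the prohibition already written in Ia and leaves granisetron and ondansetron available under the Ib caution. It adds no patients, visits, tests or analyses.

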Appendix II: ECOG Performance Status

ECOG Performance Status Scale	
Grade	Descriptions
0	Normal activity. Fully active, able to carry on all pre-disease performance without restriction.
1	Symptoms, but ambulatory. Restricted in physically strenuous activity, but ambulatory and able to carry out work of a light or sedentary nature (e.g., light housework, office work).
2	In bed <50% of the time. Ambulatory and capable of all self-care, but unable to carry out any work activities. Up and about more than 50% of waking hours.
3	In bed >50% of the time. Capable of only limited self-care, confined to bed or chair more than 50% of waking hours.
4	100% bedridden. Completely disabled. Cannot carry on any self-care. Totally confined to bed or chair.
5	Dead.

Appendix III: Patient Medication Diary

Name _____

Study No. MC1483

Patient No. _____

Please complete this diary on a daily basis. You will take the study medication (midostaurin) twice a day and you should take the medicine at about the same time in the morning and in the evening each day. Do not miss any capsules. Midostaurin capsules should be administered orally, twice daily at the same time every day and together with food. If the pills are thrown up, this should be noted on your diary but you should not take another pill until your next scheduled dose. Complete non-shaded regions if you are taking midostaurin on days 8-21. Complete all regions if you are taking midostaurin daily.

Day	Date (mm/dd/yy)	midostaurin			
		Time taken	Meal time	Dose in mg	Number of tablets
1		a.m.	a.m.		
		p.m.	p.m.		
2		a.m.	a.m.		
		p.m.	p.m.		
3		a.m.	a.m.		
		p.m.	p.m.		
4		a.m.	a.m.		
		p.m.	p.m.		
5		a.m.	a.m.		
		p.m.	p.m.		
6		a.m.	a.m.		
		p.m.	p.m.		
7		a.m.	a.m.		
		p.m.	p.m.		
8		a.m.	a.m.		
		p.m.	p.m.		
9		a.m.	a.m.		
		p.m.	p.m.		
10		a.m.	a.m.		
		p.m.	p.m.		
11		a.m.	a.m.		
		p.m.	p.m.		
12		a.m.	a.m.		
		p.m.	p.m.		
13		a.m.	a.m.		
		p.m.	p.m.		
14		a.m.	a.m.		
		p.m.	p.m.		

Day	Date (mm/dd/yy)	midostaurin			
		Time taken	Meal time	Dose in mg	Number of tablets
15		a.m.	a.m.		
		p.m.	p.m.		
16		a.m.	a.m.		
		p.m.	p.m.		
17		a.m.	a.m.		
		p.m.	p.m.		
18		a.m.	a.m.		
		p.m.	p.m.		
19		a.m.	a.m.		
		p.m.	p.m.		
20		a.m.	a.m.		
		p.m.	p.m.		
21		a.m.	a.m.		
		p.m.	p.m.		
22		a.m.	a.m.		
		p.m.	p.m.		
23		a.m.	a.m.		
		p.m.	p.m.		
24		a.m.	a.m.		
		p.m.	p.m.		
25		a.m.	a.m.		
		p.m.	p.m.		
26		a.m.	a.m.		
		p.m.	p.m.		
27		a.m.	a.m.		
		p.m.	p.m.		
28		a.m.	a.m.		
		p.m.	p.m.		

Participant's Signature: _____ Date: _____

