4.0 Test Schedule

All routine assessments must be performed within ± 7 days of the day indicated on the Visit Schedule.

Tests and procedures	Pre-Treatment	Active Treatment					
	≤ 7 days prior to registration*	Cycle 1, Day 1	Cycle 1, Day 8	Cycle 1 Day 21	Cycles 2 and above, Day 1	Cycles 2 and above, Day 8 ⁷	Early Discontinuation or End of Treatment
History and exam, weight, vitals, PS	X	X			X	X	X
Height	X						
Adverse event assessment	X	X			X		X
BM testing ²	X				X ²		X
Biomarkers FLT3 Mutation by PCR	X						X
Pregnancy Test	X						
Hematology group(CBC) Hgb, , PLT, WBC with diff. ¹	X	X ¹	X	X	X ¹	X	X
Serum Chemistry (magnesium, potassium, phosphorus, total bilirubin, direct bilirubin ⁵ , alkaline phosphatase, AST, ALT, creatinine)	X	X	X	X	X	X	X
Serum Chemistry (Serum Amylase & Lipase)	X	X			X		X
MUGA/Echo	X						
LDH	X						
Urine analysis (proteinuria, hematuria) ^R	X						
ECG (QTcF results preferred) ^{R 3}	X		X			X ³	X
Patient Medication Diary (Appendix III ⁴)			X		X	X	
Research Correlatives ^{R, 6}	X		X		X ⁶		

* Labs done on the same day of consent but prior to consenting do not need to be repeated.

1. CBC will be done weekly for cycle 1-4. After cycle 4, to be performed Day 1 and Day 8.
2. Bone marrow (BM) sampling will be done upon screening, and day 1 of cycle 3, 5, 9 and then as clinically needed. Recent bone marrow within 21 days (even prior to consenting) will be acceptable and FLT3 PCR could be done on peripheral blood if blasts >10%. Outside FLT3

testing at bone marrow biopsy will be allowed and used if done.

3. ECGs will be performed locally at screening, Day 8 (prior to dosing) of each cycle, and when there's any dose change due to QTc prolongation or re-initiation after a dose interruption. When a dose change occurs due to QTc prolongation or upon re-starting midostaurin, an ECG must be obtained at 7 days afterwards. QTcF results are preferred, however all reporting methods will be accepted.
 4. The diary must begin the day the patient starts taking midostaurin and must be completed per protocol and returned to the treating institution OR compliance must be documented in the medical record by any member of the care team. Patients will be asked to return all unused medication at each visit.
 5. Get direct bilirubin if total bilirubin > upper normal limit.
 6. Correlatives for blood and bone marrow. See section 14.

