 7. If midostaurin is started on day 1, then do these tests on day 1. If midostaurin is started on day 8, then do these tests on day 8.
- R Research funded (see Section 19.0). This will be charged to study and not to patient's account.

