7.0 Protocol Treatment

7.1 Treatment Schedule

- 7.11 Patients eligible for the study based on screening tests will be enrolled on the study.
- Patients will proceed to next cycle every 28 days (or later) based on investigator opinion when reviewing each case based on hematological and physical findings.
 - Patients who tolerate combination therapy well and fail to achieve CR/CRi/PR/morphologic leukemia-free state by end of cycle 2, could get midostaurin on days 1-28 of each subsequent cycle, rather than just days 8-21, as per treating MD decision.
 - Patients who achieve a CR/CRi/PR/morphologic leukemia-free state by end of cycle 8 will continue on current regimen.
 - Patients who fail to achieve a CR/CRi/PR/ morphologic leukemia-free state in bone marrow blasts by end of cycle 8 will go to event monitoring.
 - Patients will get a repeat bone marrow biopsy on day one of cycles 3, 5, 9 and then as clinically indicated (see Test Schedule, section 4.0). Patients who achieve CR/CRi will not need repeat bone marrow assessment unless deemed necessary by investigator.
 - Hydroxyurea and/or leukocytapheresis use is allowed to control rising blasts as deemed necessary by treating investigator at any

time.

Cycle length = 28 days (+/- 7 days)

Agent	Dose	Route	Day	Comments
Decitabine ¹	20 mg/m ²	IV	1-5	Could be given days 2-5 by local MD (outside Mayo Clinic).
Midostaurin ²	50 mg twice/day	Oral	8-21	Midostaurin could be given continuously (day 1-28) starting cycle 3 based on MD decision (see 7.11).

1. May be held as per treating physician judgment.
2. If decitabine is held, then midostaurin will be held. If decitabine is administered, midostaurin cannot be held, but can be omitted.

7.12 Maximum cycles of midostaurin are 18, after which a discussion with Novartis will be done on a per patient basis whether to keep patient on continued therapy with the combination of decitabine and midostaurin on study (continue active monitoring per section 4.0).

7.13 If midostaurin is discontinued, single agent Decitabine may be given beyond cycle 18 off protocol until relapse or disease progression off protocol. The patient will go to event monitoring per section 18.0

Note: If single agent Decitabine is being given off protocol, the end of active treatment form should be filled out at the end of cycle 18. Reason treatment ended should be reported as treatment completed per protocol criteria.

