Other Non-hematological	Grade 4 Non-Hematologic		Discontinue midostaurin for non-hematologic grade 4 toxicity (including grade 4 vomiting, diarrhea, and pneumonitis). Midostaurin should be held for other non-hematologic grade 3 toxicity until recovery to \leq Grade 2. Upon recovery, the patient may restart dosing. If additional toxicity recurs, the midostaurin dose will be reduced to 25mg b.i.d. In the event of additional toxicity requiring dose modification, further dose reductions to midostaurin 25mg Q.D. will be allowed. If the patient tolerates the lower dose of midostaurin (25 mg b.i.d), a dose increase back to 50mg b.i.d may be attempted as tolerated. Fatigue and hair loss are exempted.

¹If decitabine is held, then midostaurin will be held. If decitabine is administered, midostaurin cannot be held, but can be omitted.

All dose modifications should be based on the worst preceding toxicity. Common Toxicity Criteria for Adverse Events (CTCAE Version 4.0)

If midostaurin is omitted due to QTc prolongation or when there's any dose change, an ECG must be obtained at 7 days afterwards.

- 8.3 Decitabine dose modification:
- Modification will be done as per standard recommendation and treating physician judgement for patient's best interest and will be mainly based on non-hematological AEs.
 - For creatinine AEs, creatinine clearance will be calculated using Cockcroft formula with total body weight and gender adjustment.

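### The Appendix III diary fixes midostaurin at twice daily, but Section 8.2 allows 25 mg once daily; at that level only, the printed frequency gives 50 mg/day instead of 25 mg/day

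*Combined protocol and SAP*

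**What the plan says.** Appendix III states the frequency twice. The patient is told "You will take the study medication (midostaurin) twice a day", in the morning and the evening, and then that "Midostaurin capsules should be administered orally, twice daily at the same time every day and together with food". Each of the 28 days has an a.m. and a p.m. row. The columns for dose and number of tablets are blank. The form explains which regions to complete under the days 8-21 and the daily schedules. It has no once-daily wording and no line for the schedule the site has assigned.

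In Section 8.2, the row for other non-hematologic toxicity starts with a hold for grade 3 events and a restart on recovery. It then says "If additional toxicity recurs, the midostaurin dose will be reduced to 25mg b.i.d". For additional toxicity after that, "further dose reductions to midostaurin 25mg Q.D. will be allowed".

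Section 4.0, footnote 4, requires the diary or, as an alternative, that "compliance must be documented in the medical record by any member of the care team". It adds that "Patients will be asked to return all unused medication at each visit". The closing note of Section 8.2 calls for an ECG 7 days after any dose change. Footnote 1 of Section 4.0 sets weekly blood counts in cycles 1 to 4.

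**The concern.** A patient at the once-daily step holds a printed sheet that gives a different frequency from the order in force. Dose per intake can vary on the form, but frequency cannot. That patient has already had toxicity, a first reduction and then further toxicity. Following the sheet would undo the last reduction step that Section 8.2 names and return the patient to the dose just judged too high. The trial enrols people aged 60 or over with ECOG status up to 3 who take capsules at home, so a patient-facing instruction should not contradict the order.

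**Working it through.** **Inputs**

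- Starting dose: 50 mg twice daily (Section 8.1).
- First reduction step: 25 mg twice daily. Second step: 25 mg once daily (Section 8.2, other non-hematologic row).
- Other named reductions: 25 mg twice daily for a second grade 4 febrile neutropenia and for QTc above 470 and up to 500 msec (Section 8.2).
- Capsule: 25 mg (15.12), swallowed whole (15.14). Two intakes a day therefore cannot deliver less than 2 × 25 = 50 mg.
- Diary frequency: two intakes a day (Appendix III).
- Maximum accrual: 26 (16.22).

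**Daily dose = mg per intake × intakes per day**

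| Level | Assigned, mg/day | At the diary's frequency, mg/day | Ratio |
|---|---|---|---|
| 50 mg twice daily | 50 × 2 = 100 | 50 × 2 = 100 | 1.0 |
| 25 mg twice daily | 25 × 2 = 50 | 25 × 2 = 50 | 1.0 |
| 25 mg once daily | 25 × 1 = 25 | 25 × 2 = 50 | 2.0 |

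Only the last row conflicts. The 50% reduction in 9.4 for a strong CYP3A4 inhibitor names no frequency and adds no new level. From 50 mg twice daily it can be given as 25 mg twice daily; from 25 mg twice daily it leads to the same 25 mg/day.

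**Extra drug if the diary's frequency is followed at once daily** (one extra 25 mg capsule a day)

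- Caught at about 7 days: 7 × 1 = 7 capsules; 7 × 25 = 175 mg.
- Uncorrected over days 8-21 (14 days): 14 × 50 = 700 mg against 14 × 25 = 350 mg. The excess is 350 mg, or 350 / 25 = 14 capsules.
- Uncorrected over days 1-28 (allowed from cycle 3 under 7.1): 28 × 50 = 1400 mg against 28 × 25 = 700 mg. The excess is 700 mg, or 700 / 25 = 28 capsules.

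**When it could be noticed**

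The Test Schedule lists the diary at cycle 1 Day 8 and at Days 1 and 8 of later cycles. On days 8-21, the next listed diary check after Day 8 is Day 1 of the next cycle. With continuous dosing, footnote 7 moves the Day 8 tests: "If midostaurin is started on day 1, then do these tests on day 1". The next check is again Day 1 of the following cycle. Between those dates there are the 7-day ECG and, in cycles 1 to 4, weekly blood counts. Neither is listed as a diary check.

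**The case against.** The strongest case is that the diary cannot work as a dosing order. It gives no milligrams and no capsule count, so the site must tell the patient what to take. The 50 mg/day figure needs a patient who accepts the 25 mg from that instruction, takes the frequency from the form instead, and has spare capsules. The once-daily step is also optional and sits in one table row behind two earlier steps. Grade 4 non-hematologic toxicity leads to discontinuation instead, and fatigue and hair loss are exempt. All of this stands, and it is why the likelihood is low. It does not remove the conflict, because the documents describe no step for marking the diary when the dose changes.

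A reader might infer that nothing could catch the error until the course is over, making 14 or 28 capsules the expected size. The documents do not support that. Section 8.2 requires an ECG 7 days after any dose change, although footnote 3 of Section 4.0 is narrower, covering QTc-related changes and restarts. Weekly blood counts and the return of unused capsules give further chances to notice. None is a guarantee: ECGs are done locally, and no diary check is tied to either test.

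It can also be said that the second diary sentence merely repeats the default frequency in 15.14. As general drug information that default is unobjectionable. But 15.191 tells staff to instruct patients on the same frequency, so correcting the diary alone would leave one instruction unqualified.

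**Conclusion.** The conflict is real, confined to the 25 mg once-daily level, and minor. At that level the diary's frequency doubles the assigned dose, 50 against 25 mg/day. The likely size if it happens and is caught at the 7-day ECG is about 7 capsules (175 mg). The larger totals are worst cases that assume a full course at once daily, the diary followed throughout, enough capsules in hand and no contact that leads to a correction.

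The documents give no rate of reaching once-daily dosing; none to a few of at most 26 patients is an assumption. That a separate site instruction always exists is inferred from the diary's blank dose columns.

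A reader might infer that the diary contradicts dose reduction in general, or that the trial's result is at risk. Neither follows. The reductions to 25 mg twice daily keep the printed frequency, and no endpoint or decision rule in Section 16 depends on the diary. This is a patient-safety correction for the next amendment, not a reason to hold the trial.

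**What to change.** In Appendix III, replace both twice-daily statements, including the morning-and-evening wording, with one line that the site completes each cycle and at any dose change: *Take __ capsule(s) of 25 mg, __ time(s) a day, on days __ to __, with food.* Tell the patient to leave unused a.m. or p.m. rows blank.

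In 15.191, after the twice-daily instruction, add *or as reduced under Section 8.2*.

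The cost is one appendix page and one phrase in the next amendment, plus a few seconds per visit to fill in the line. No dose or reduction rule changes.
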